5.5.2 Treatment Day 1 – in Cardiac Catheterization Lab and Recovery

- Random allocation to study drug (once screening is complete and consent is obtained either from the subject or a legally authorized representative of the subject, randomization must occur to ensure study drug is given by bolus injection between an hour prior to and 5 minutes prior to coronary reperfusion, so as to be complete at least 5 minutes prior to reperfusion)
- Study drug administration
- Vital signs (pulse, respiratory rate, blood pressure) will be recorded every 15 minutes after study drug for an hour, then hourly for another 4 hours. There is a +/- 10 minute window on all vital sign collections
- Blood sampling to assess anticoagulation during the procedure (INR)
- Documentation of peri-procedural arrhythmias by medical staff by 12-lead ECG
- Continuous ECG monitoring will commence post procedure as soon as the 7 day wearable device can be affixed to the patient and up to 14 days post study drug¹
- Standard 12 lead ECG prior to treatment to obtain baseline ST-segment elevation and again at 4 hours post-study drug to assess ST segment resolution (3 strips at each time point)
- Blood samples for troponin T will be obtained (see time points in Section 12)
- PK blood sampling (see time points in Section 12)
- Blood sample to assess biomarkers of cardiac injury and inflammation (see time points in Section 12)
- Laboratory safety tests (as outlined in Section 12)
- Recording of concomitant medications
- Recording of any AEs
- If study informed consent was given by the subject's legally authorized representative for study enrollment, the subject will be provided with a modified consent once they are stable (after investigational drug treatment and STEMI procedure) and

in the opinion of the investigator capable of providing written consent. This modified informed consent document will cover the subject's agreement to remain in the clinical trial and proceed with all study related procedures and follow-up.

¹ The wearable ECG monitor device should be affixed to the patient as soon as possible post-study drug. This single-use device will need to be removed when the patient undergoes CMR at 72 +/- 24 hours post-study drug. At that time, a new wearable ECG monitor device will need to be affixed to the patient.

5.5.3 Day 2 (24 hours +/- 2 hours post-study drug)

- Physical examination and vital signs (pulse, respiratory rate, blood pressure)
- Laboratory safety tests (as outlined in Section 12)
- Blood samples for troponin T will be obtained (see time points in Section 12)
- PK blood sampling (see time points in Section 12)
- Blood sample to assess biomarkers of cardiac injury and inflammation (see time points in Section 12)
- Recording of any AEs
- Concomitant medications

5.5.4 Day 3 (48 hours +/- 2 hours post-study drug)

- Physical examination and vital signs (pulse, respiratory rate, blood pressure)
- Laboratory safety tests (as outlined in Section 12)
- Blood samples for troponin T will be obtained (see time points in Section 12)
- Blood sample to assess biomarkers of cardiac injury and inflammation (see time points in Section 12)
- Recording of any AEs
- Concomitant meds

5.5.5 First CMR (72 hours +/- 24 hours post-study drug)

- CMR to measure MSI, INF/VV, INF and cardiac function including EDV, ESV, FS and EF. If CMR cannot be completed at the time of discharge, the patient should be encouraged to return for a CMR 48-96 hours post-study drug.
- Physical examination and vital signs (pulse, respiratory rate, blood pressure) (at time of discharge)
- Recording of any AEs (at time of discharge)
- Concomitant medications (at time of discharge)

- Discharge with instructions for continuous ECG device (at time of discharge)²

² Instructions for the wearable ECG monitoring device will be given prior to discharge. The wearable ECG monitoring devices can collect data for 7 days therefore, a follow up phone call will be conducted 7 days after the wearable ECG monitoring device was first affixed to the patient to ensure compliance with removing the wearable ECG monitoring device and replacing it with another one. Instructions will also be given at that time on retaining the first week's data for return to the clinic at day 14.

5.5.6 Follow-up 14 days (+/- 2 days post drug)

- Physical examination and vital signs (pulse, respiratory rate, blood pressure)
- Body weight (kg)
- Laboratory safety tests (as outlined in Section 12)
- Recovery of wearable ECG devices and recordings
- Recording of any AEs
- Concomitant medications

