4.1 Primary Outcome

The primary outcome for this study will be the combined number and incidence rate of several arrhythmias of interest that occur in each group over a 14 day period post-study drug. These arrhythmias including ventricular fibrillation, sustained ventricular tachycardia (≥ 125 BPM, ≥ 30 seconds), non-sustained ventricular tachycardia (≥ 125 BPM, ≥ 16 beats, < 30 seconds) and high degree AV block (2nd or 3rd degree, ≥ 8 beats) were chosen because they are significant prognostic indicators of depressed left ventricular ejection fraction and cardiac death [1]. The combined number of arrhythmic events in each group will be calculated along with the arrhythmia incidence rate defined as the percentage of patients in each group experiencing at least one of the defined arrhythmias of interest.

An exploratory sub-analysis will be conducted to determine the number and incidence rate of each separate arrhythmia type per dose group.

Continuous cardiac monitoring will occur for 14 days post PCI by means of wearable patch devices.

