11 STUDY OUTCOMES

Primary Outcome: The primary outcome for this study will be the combined number and incidence rate of several arrhythmias of interest that occur in each group over a 14 day period post-study drug.

These arrhythmias including ventricular fibrillation, sustained ventricular tachycardia (≥ 125 BPM, ≥ 30 seconds), non-sustained ventricular tachycardia (≥ 125 BPM, ≥ 16 beats, < 30 seconds) and high degree AV block (2nd or 3rd degree, ≥ 8 beats) were chosen because they are significant prognostic indicators of depressed left ventricular ejection fraction and cardiac death [1].

The combined number of arrhythmic events in each group will be calculated along with the arrhythmia incidence rate defined as the percentage of patients in each group experiencing at least one of the defined arrhythmias of interest.

An exploratory sub-analysis will be conducted to determine the number and incidence rate of each separate arrhythmia type per dose group.

Continuous ECG monitoring will occur from post reperfusion until 14 days post study drug by means of wearable ECG recorders. These will be positioned and activated as soon as feasible after treatment with study drug is complete.

Blinded, standardized centralized interpretation will be used for analysis of arrhythmias recorded with the wearable device.

Descriptions of peri-procedural arrhythmias such as reperfusion arrhythmias or VF episodes occurring prior to application of the wearable cardiac monitor will be categorized and documented separately on the CRF, with particular emphasis on persistent arrhythmias.

Secondary Outcomes:

- Infarct size parameters will be assessed by CMR at 72 +/- 24 hours and at 3 months; the following will be compared between groups; infarct size as a proportion of ventricular volume (INF/VV), myocardial salvage index (MSI) and absolute MI size
- The proportion of patients with ST-segment resolution at 4 hours post study drug
- Serum levels of troponin calculated as AUC 0-48 hours post-study drug

- Serum biomarkers of cardiac injury, inflammation and remodeling out to 3 months of follow up
- Persistent arrhythmias at 30 days and 3 months
- Measures of cardiac function by CMR including EDV, ESV, FS and EF
- Cardiac-related adverse events including the development of heart failure out to three months of follow up.

Incidence of all-cause and cardiac mortality out to 6 months of follow up

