13 CHANGES FROM THE PROTOCOL SPECIFIED STATISTICAL ANALYSES

For the analysis of arrhythmias of interest, a person-time adjustment will be applied to account for potential missing data during the 14-day monitoring period, due to possible unforeseen reasons such as patient withdrawal, device failure or death. The incidence rate for each treatment group (and overall FDY-5301) will be calculated as the number of events divided by the total person-time of monitoring within each treatment group. The incidence rate ratios of each treatment group (and overall FDY-5301) versus the placebo will be derived.

Scope of the interim analyses has been updated.

Overall summary for primary and exploratory safety and efficacy endpoints will be summarized by stratification of TIMI flow grade and infarct location

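### The Day 14 visit window lets sites collect the ECG patches up to 2 days before the 14-day arrhythmia monitoring period ends

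*Protocol*

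**What the plan says.** Protocol Section 4.1 defines the primary outcome as the number and incidence of "arrhythmias of interest that occur in each group over a 14 day period post-study drug". Protocol Section 11 sets the recording period to match: "Continuous ECG monitoring will occur from post reperfusion until 14 days post study drug by means of wearable ECG recorders". Neither gives a tolerance.

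The visit that closes this period is Protocol Section 5.5.6, "Follow-up 14 days (+/- 2 days post drug"; Table 2 shows the same window. One of its listed tasks is "Recovery of wearable ECG devices and recordings". The footnote to Section 5.5.5 points the same way, asking patients to keep the first week's "data for return to the clinic at day 14". That footnote also says each device records for 7 days and is to be replaced after a call made 7 days after the first fitting.

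In the SAP, Section 11.4.1 calculates the incidence rate as events divided by recorded person-hours, split into the first 48 hours from the start of PCI (Period 1) and the rest (Period 2). Section 13 explains that this adjustment is for monitoring data missing "due to possible unforeseen reasons such as patient withdrawal, device failure or death".

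**The concern.** The endpoint period ends at 14 days, but the visit at which the recorder is handed in may take place at 12. A site that keeps to the schedule can therefore stop primary-outcome recording before the period is over, and neither document tells it how to handle a patient who comes early.

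What is lost is the tail of the monitoring period. Protocol Section 14.1.4 says the main aim is to describe arrhythmias over 14 days after infarction and to find out whether patches can capture them. Hours lost because a visit was booked early count against both aims, and make patch capture look less complete than the device itself would have made it.

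**Working it through.** **Inputs.** Endpoint and monitoring period 14 days after study drug (Protocol 4.1, 11). Visit window 14 +/- 2 days, with device recovery at that visit (Protocol 5.5.6, Table 2). Device capacity 7 days, replaced 7 days after first fitting (Protocol 5.5.5 footnote). Period 2 runs from 48 hours to 14 days (SAP 11.4.1). The plan states no figure for this loss, so there is none to reproduce.

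**1. Hours lost to the window alone.** Planned period: 14 x 24 = 336 h. Period 2: 336 - 48 = 288 h, treating study drug and the start of PCI as the same moment.

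| Visit (days after drug) | Hours possible | Lost | Share of 336 h | Share of Period 2 |
|---|---|---|---|---|
| 12 | 288 | 48 | 14.3% | 16.7% |
| 13 | 312 | 24 | 7.1% | 8.3% |
| 14 to 16 | 336 | 0 | 0% | 0% |

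The protocol labels 24 hours as Day 2, so 12 days after drug is strictly study Day 13. The shortfall is the same.

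**2. Does the device force the loss?** No. A device fitted on Day 1, changed at the first CMR and changed again 7 days after first fitting can record to about 7 + 7 = 14 days.

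**3. Average loss.** The documents give no distribution of visit days, so the mean lies anywhere from 0 days (nobody early) to 2 days (everybody at 12). If visit day T were uniform on 12 to 16 (assumption), half of patients would be early, by 1 day on average: E[max(0, 14 - T)] = 0.5 x 1 = 0.5 day, and 0.5/14 = 3.6%.

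**4. What the person-time rate corrects.** Let the event rate be a up to 12 days and r x a from 12 to 14 days. If every patient were seen at 12 days, the observed rate is a and the full-period rate is (12a + 2ra)/14. Observed over full = 14/(12 + 2r).
- r = 1: 14/14 = 1, an exact correction.
- r = 0.5: 14/13 = 1.08, so the rate is overstated by about 8%.
- r = 0: 14/12 = 1.17, so it is overstated by about 17%.

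The values of r are illustrations. If r and the visit pattern are the same in two arms, the factor cancels from the rate ratio.

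**5. What it does not correct.**
- Combined event count: no denominator. With a constant rate and every visit at 12 days, 2/14 = 14.3% of events would be missed. If events cluster early, fewer.
- Time-to-last-event: SAP 11.4.1 censors only patients with no event. A patient with events at, say, 5 and 13 days whose patch is collected at 12 enters as an uncensored time of 5 days.

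**The case against.** The strongest reply is that the SAP already deals with unequal recording. Its person-time is actual recording time, whatever the cause of a shortfall; the causes listed in SAP Section 13 are examples. Event-free patients are censored when their recording stops. This largely stands for the incidence rate and the rate ratio. It does not reach the raw count or time-to-last-event, and a visit inside the permitted window is foreseeable, unlike the losses the SAP describes.

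A second reply is that Protocol Section 11 already fixes the end of monitoring, so a careful site would leave the patch on. But Section 5.5.6 tells the same site to take the device back at the visit, and Section 5.5.2 describes monitoring more loosely, starting "as soon as the 7 day wearable device can be affixed to the patient and up to 14 days post study drug". The passages need reconciling.

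Some of the opposing case stands in full. The primary outcome is descriptive, with no hypothesis test (Protocol 14.1.6). No sample size or power figure depends on this point. The lost time falls wholly in Period 2, not in the first 48 hours.

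**Conclusion.** The conflict is real and avoidable: a compliant visit can cost up to 48 of 336 hours of primary-outcome recording per patient. The maximum follows from the text alone; any average rests on an assumed spread of visit days. The consequence is lost late data, a lower event count, truncated last-event times and some added variability. It is a cheap improvement, not a threat to the trial.

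A reader might infer more, and the documents do not support it:
- **Bias between arms.** The window is the same in every arm and the trial is double-blind. A chance imbalance in visit days is what the person-time denominator is there to absorb. The analysis uses the ITT population (SAP 11.4), which with up to 160 randomised 1:1:1:1 is up to 160/4 = 40 per arm, not the 20 of the evaluable target.
- **Damage to the percentage of patients with at least one event.** That is the protocol's incidence measure. SAP Section 4 says the SAP supersedes the protocol's statistical considerations, and Sections 11.4.1 and 13 replace the percentage with events per person-time.
- **Early attenders becoming non-evaluable.** The protocol synopsis asks for a complete arrhythmia dataset but does not define that as 336 recorded hours. Read that way, almost nobody would qualify, because the patch goes on only after the procedure and comes off for CMR. The SAP populations have no recording-completeness criterion.

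**What to change.** In Protocol Section 5.5.6 and Table 2, set device recovery at 14 days (-0/+2 days), and state that the last device stays on until 14 x 24 hours after study drug. The upper half of the window can stay: a visit at 14 to 16 days loses nothing, and only the 14-day period is counted.

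The cost is a short amendment and the two days of scheduling flexibility before Day 14. A patient who must attend early would have to keep the device and return it later. The documents describe no route for that, so the amendment should name one. Waiting for the 30-day visit would avoid an extra trip but could delay the 14-day arrhythmia analysis planned in Protocol Section 14.1.5 and SAP Section 12.

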5.5.7 Follow-up 30 days (+/- 1 week post drug)

- Physical examination and vital signs (pulse, respiratory rate, blood pressure)
- Body weight (kg)
- Laboratory safety tests (as outlined in Section 12)
- 12-lead ECG including rhythm strip to identify persistent arrhythmias
- Recording of any AEs
- Concomitant medications

5.5.8 Follow-up 3 months (+/- 2 weeks post drug)

- CMR to measure MSI, INF/VV, INF and cardiac function including EDV, ESV, FS and EF
- Recording of any AEs
- Concomitant medications
- 12-lead ECG including rhythm strip to identify persistent arrhythmias
- Blood sample for analysis of biomarkers of remodeling

5.5.9 Follow-up 6 months or early termination (+/- 4 weeks post drug)

Telephone interview with the subject (or relative if subject unable to give history) for incidence of all cause and cardiac mortality. If subject is unavailable, then physician/investigator records will be source of mortality documentation if available.

Figure 1: Study Diagram

Table 2: Study Design and Schedule of Assessments

Activity	Screening	Treatment	Day 2 (24 +/- 2 Hrs)	Day 3 (48 +/- 2 Hrs)	First CMR (72 +/-24 Hrs)	Day 7	14 day (+/- 2 days)	30 day (+/- 1 week)	3 month (+/- 2 weeks)	6 month/Early Termination (+/- 4 weeks)
	Day 1	Day 1								
Inclusion/Exclusion Criteria, IC¹⁴	X									
Demographics/Medical History	X									
Physical Examination(including Con medss)	X		X	X	X		X	X	X	
Vital Signs, con meds	X	X ¹⁰	X	X	X		X	X	X	
Height and Weight	X									
Safety Laboratory tests		X ³	X	X			X	X		
Troponin T		X ⁴	X	X						
Randomization, study drug			X							
ACT during anticoagulation			X							
Document peri-proc. arrhythmias			X							
Continuous ECG										
Phone call re continuous ECG							X			
12 lead ECG	X	X ¹¹						X ¹²	X ¹³	
PK-Iodide levels		X ⁵	X	X						
Cardiac Biomarkers		X ⁶	X	X					X	
CMR					X ⁷				X	
Adverse Events	X	X	X	X	X		X	X	X	

Follow up phone call or review of physician records for all-cause mortality									X
Un-blinded Interim Analysis							X ⁸	X ⁹	

3. Safety Lab Sampling for day 1: Pre-study drug, 4 and 12 hours post-study drug
4. Troponin Sampling for day 1: Pre-study drug, and 12 hours post-study drug
5. PK Sampling for day 1: Pre-study drug, 2 minutes post-study drug, 1 and 4 hours post-study drug
6. Biomarker Sampling for day 1: Pre-study drug, 1, 4 and 12 hours post-study drug
7. CMR should be conducted 48-96 hours post-study drug preferably before patient is discharged from hospital.
8. Unblinded analysis of CMRs, 14-day arrhythmias, Troponin levels and ST-segment resolution will be conducted by a separate unblinded team at Covance and rest of Covance study team, Faraday, Investigators, and 3rd party vendors will not be unblinded to individual patient treatments
9. Unblinded analysis of CMRs will be conducted by a separate unblinded team at Covance and rest of Covance study team, Faraday, Investigators, and 3rd party vendors will not be unblinded to individual patient treatments
10. Vital signs (pulse, respiratory rate, blood pressure) will be recorded every 15 minutes after study drug for an hour, then hourly for another 4 hours. There is a +/- 10 minute window on all vital sign collections
11. 12-lead ECG for day 1: at screening for diagnosis of STEMI for inclusion criteria, and to obtain baseline ST-segment elevation, during PCI treatment to document peri-procedural arrhythmias and again at 4 hours post study drug for ST-segment resolution. 3 strips each at screening and 4 hour time point
12. 12-lead ECG including rhythm strip to identify any persistent arrhythmias
13. 12-lead ECG including rhythm strip to identify any persistent arrhythmias
14. Prior to study enrollment written informed consent will be obtained either from the subject or a legally authorized representative of the subject. If study informed consent was given by the subject's legally authorized representative prior to study enrollment, the subject will be provided with a modified consent once they are stable (after investigational drug treatment and STEMI procedure) and in the opinion of the investigator capable of providing written consent. This modified informed consent document will cover the subject's agreement to remain in the clinical trial and proceed with all study related procedures and follow-up.

6 SELECTION AND WITHDRAWAL OF SUBJECTS

The subject or a legally authorized representative must have provided informed consent after the nature of the study has been explained and questions addressed. Subjects must meet the following criteria to be eligible to participate in the study.

6.1 Subject Inclusion Criteria

2. 18-80 year old male subjects
3. 18 to 80 year old female subjects who are not of child-bearing potential.
4. Accepted for Primary PCI with diagnosis of first STEMI, based on clinical and ECG criteria (ST-elevation at the J-point in two contiguous leads with the cut-off points: ≥ 0.2 millivolt (mV) in men or ≥ 0.15 mV in women in leads V2-V3 and/or ≥ 0.1 mV in other leads), within 12 hours of symptom onset.

Written informed consent prior to study participation (either by the subject or a legally authorized representative of the subject)

6.2 Subject Exclusion Criteria

1. Previous myocardial infarction
2. Left bundle branch block (LBBB)
3. Previous coronary artery bypass graft surgery (CABG)
4. Major hemodynamic instability or uncontrolled ventricular arrhythmias.
5. Known contraindication to CMR (e.g. pacemaker)
6. Patients with known thyroid disease, or known allergy to iodide.
7. Subjects with past or current renal impairment requiring dialysis
8. Pregnant or females of child bearing potential
9. Body weight > 120 kg or Body Mass Index (BMI) > 35 kg/m²
10. Use of investigational drugs or devices within 30 days prior to enrollment into the study.
11. Life expectancy of less than 1 year due to non-cardiac pathology
12. Any clinically significant abnormality identified at the time of screening that in the judgment of the Investigator or any sub-Investigator would preclude safe completion of the study

6.3 Subject Withdrawal Criteria

Subjects have the right to withdraw from the study at any time and for any reason without prejudice to his or her future medical care by the physician or at the Institution. Subjects may also be withdrawn from the study at the discretion of the PI.

Any subject who withdraws consent to participate in the study will be removed from the study. Although the subject is not obliged to give his or her reason for withdrawing prematurely from the study, the Investigator should make a reasonable effort to ascertain the reasons while fully respecting the subject's rights.

In the interest of the subject, subjects who withdraw consent or are withdrawn from the study by the Investigator should be encouraged to complete a follow-up visit (early termination visit) as soon as possible and an effort should be made to complete and report the observations as thoroughly as possible up to the date of withdrawal. All information should be reported on the applicable CRF.

6.4 Early Termination Visit

At any such early termination visit, the procedures scheduled for the six-month follow-up should be performed.

7 STUDY TREATMENTS

7.1 Description of Study Drug

FDY-5301 is sodium iodide (chemical formula NaI) administered as an isotonic solution for intravenous injection with a concentration of 7.2 mg/mL. The dosage form of FDY-5301 is a small volume parenteral solution. The solution has a pH between 7.0 and 9.5. Normal saline will be used as placebo.

